			43.1 Rales Y N
	38.1 1bs.		43.2 Edema
	38.2 kg.		43.3 Elevated jugular venous pressure Y N

•

Any of the following present? (cont.) Yes No	49. Amplitude of R wave in AVL:
43.4 S3 gallop Y N	50. Amplitude of R wave in II, III, or AVF (whichever is larger):

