### B. Subsidiary Objectives:

The subsidiary objectives of the Registry are:

1. To study cardiovascular mortality at one, three and five years globally and after stratification according to symptoms, etiology of disease, ejection fraction and chest X-ray findings in the above populations.

2. To study morbid events at one year in the above population.

3. To relate other baseline covariates of prognostic importance to subsequent mortality and morbidity in the above population.

4. To characterize in greater detail clinical characteristics, echocardiographic abnormalities, arrhythmia status, functional capacity and neurohumoral levels and to correlate these detailed findings with subsequent mortality and morbidity in a stratified randomly selected sample of 1000 patients from among the patients entering the Registry.

5. To compare baseline characteristics and follow-up events of this relatively unselected population with those of the SOLVD Trials.

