# VII. DETAILED INVESTIGATIONS IN A SUBSAMPLE OF 1000 PATIENTS (REGISTRY SUBSTUDY)

Since there is no uniform requirement of investigations other than ejection fraction or chest X-ray in the Registry, it is possible that some of the data collected from the hospital records may be biased (e.g., more tests done on the "sickest" patients). In order to obtain key data on a relatively "unselected population" that differs from the Trials substudy population and to assess the biases inherent in the main body of the Registry, 1000 stratified (see appendix D) randomly chosen patients will be studied. The following procedures are to be completed:

- M-mode and 2-D echocardiograms (to be read centrally). Doppler i) echocardiograms would be performed only at those centers participating in the SOLVD Echocardiography Substudy.
- Physical examination and history. ii)
- Drawing of blood for plasma renin and catecholamines iii) (determinations to be performed centrally).
- Seventy-minute ambulatory Holter monitoring (one hour at rest, iv) during the 6-minute walking test, and for 3 minutes post walking) (to be read centrally).
- Six-minute walking test. v)
- Chest X-ray and electrocardiogram, if not done within 90 days. vi)

Once a patient has entered the Registry, the SOLVD microcomputer data entry system will identify whether a particular patient is to be selected for the Registry Substudy. Once such a patient is identified, he/she is invited to participate in the Registry Substudy. If he/she consents and a good quality (as defined in Appendix C) echocardiogram is obtained, all the other tests are performed. If he/she refuses or a good quality echo cannot be obtained, this patient does not enter the substudy but should still be included in the main Registry. The flowchart in appendix A2 describes the procedure for the Registry Substudy clinic visit. Preferably, the visit is to be scheduled for the day the echocardiogram can be performed. If this is not possible, the echo and the rest of the procedures must be done within two weeks of each other and any major intercurrent events occurring must be documented with a Hospitalization form. The clinic visit should take place no later than 90 days after enrollment.

A brief description of each procedure follows; for details on their protocols, see Appendix C.

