10.3 State/Province:	12.2 Hospital street address:
10 4 Country:	

12.3 City:	14.2 First Name:
	15.1 Street address:
12.4 State/Province:	
12.5 Country:	
12.6 Zip Code/Canadian or European Postal Code:	15.2 City:
13. Patient hospital ID number:	
PRIVATE PHYSICIAN INFORMATION	15.3 State/Province:
14.1 Last Name:	15.4 Country:
	15.5 Zip Code/Canadian or European Postal Code:

4

SOLVD MAIN REGISTRY BASELINE FORM (screen 5 of 15) (RBF page 3 of 8)

•

16. Telephone Number (private physician):	19.1 Street address:
NEAREST RELATIVE OR FRIEND NOT RESIDING WITH PARTICIPANT	
17.1 Last name:	
	19.2 City:
17.2 First name:	
18. Relationship:	

(Nearest relative/friend continued)	D. X-RAY FINDINGS Ye	s
19.3 State/Province:	<pre>21.1 Is chest-X-ray available? Y    (If NO, skip to section E)</pre>	
19.4 Country:	21.2 Date of most recent chest X-ray (should be 7 or more days after MI, cardiac sur- gery, PTCA, or balloon valvuloplasty): ////// Month Day Year	
20. Telephone number:	21.3 Is this X-ray the qualifying X-ray? Y	
	22. Pulmonary congestion:	
	22.1 Evidence of pulmonary congestion Y (If NO, skip to Q. 23)	!
	22.2 Basal or perihilar vascular blurring	!
	22.3 Kerley B lines Y	!
	(continued)	

Т

SOLVD MAIN REGISTRY BASELINE FORM (screen 7 of 15) (RBF page 4 of 8)

	Y	es	No			Yes	No	Unreco
	Alveolar or pulmonary edema		N	24.	Indicate all of the following th rently (including etiology speci	at o fied	ccur abo	concur ve):
22.5	Pleural effusion	Y	N	24.1	Ischemic heart disease (IHD)	Y	N	U
E.	ETIOLOGY OF DISEASE	223		24.2	Hypertensive heart disease (HHD)	¥	N	U
23.1	What is the primary etiology of participa heart disease (choose only one of the fol	int's	ng):	24.3	Active myocarditis	Y	N	U
	Ischemic heart disease (IHD)		1	24.4	Idiopathic cardiomyopathy	¥	N	U
	Hypertensive heart disease (HHD)		2	24.5	Specific cardiomyopathy (ex: viral, toxic, ETOH, post-	Y	N	U
	Active syocarditis		3		partum, history of cocaine use) (If NO or UNRECORDED, skip to Q.	24.	7)	
	Valvular heart disease - aortic		4	24.6	Specify:			
	Valvular heart disease - mitral		5	24.7	Valvular heart disease - aortic	Y	N	U
	Idiopathic cardiomyopathy (specifics unknown)		6	24.8	Valvular heart disease - mitral	Y	N	U
	Specific cardiomyopathy (ex: viral, toxic, ETOH, postpartum, history of cocaine use) (If none, skip to Q. 24)		7					
23.2	Specify:		-		•			

-----

F. RELATIONSHIP TO SOLVD TRIALS (SKIP TO SEC G IF EF> 35%)		Yes	No	Unreca
	26.3 Complex congential heart disease	Y	N	U

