28.5 Angina pectoris	¥	N	U	29.2	Enter date of most recent myoca	TUIAI		arce101
28.6 Peripheral embolism	Y	N	U		Month Year			
28.7 Pulmonary embolism	¥	N	U	29.3	Was the MI complicated by pulmo	narv	edem	۵.
28.8 Syncope	¥	N	U		shock, or heart failure?	Y	N	, n
28.9 Hypertension	Y	N	U					

SOLVD MAIN REGISTRY BASELINE FORM (screen 11 of 15) (RBF page 6 of 8)

٠

----

. .... . . .**...** 

30.	Smoking history	Yes	No	Unrecorded	Yes No Unreco
30.1	Has the participant ever been a smoker (tobacco)? (If NO or UNRECORDED, skip to Q.	¥ 31)	N	U	32. Permanent pacemaker? Y N U
30.2	Does the participant currently smoke?		N	U	33. Use of automatic implantable defibrillator? Y N U
31.	Alcohol consumption history	•	M	U I	34.1 Previous cardiac surgery, PTCA, or balloon valvuloplasty? Y N U (If NO or UNRECORDED, skip to Q. 35)
31.1	Has the participant ever regular consumed alcohol? (If NO, skip to Q. 32)		N	U	34.2 Enter date of most recent cardiac surgery, PTCA, or balloon valvuloplasty:
31.2	Is there history of alcohol abuse? (See Manual of Operations for guidelines)		N	υ	Month Year
31.3	Does the participant currently consume alcohol?	Y	N	υ	

ł

- -

	Type of cardiac surgery:	Yes	No	Unre	corded			2	les	No
34.3	Coronary artery bypass graft	¥	N	U	ſ		36.2	Potassium-sparing diuretic	Y	N
34.4	Valve replacement - aortic	¥	N	U	l			Antiarrhythmic drug other than bet blocker or calcium antagonist	ra- Y	N
34.5	Valve replacement - mitral	Y	N	U			36.4	Regular use of antiplatelet	Y	N
34.6	Percutaneous transluminal coronary angioplasty (PTCA)	Y	N	U	1		36.5	Beta-blocker	Y	N
34.7	Balloon walwuloplasty	Y	N	U	I		36.6	Long-acting oral nitrate or paste	Y	N
34.8	Other	Y	N	U	I		36.7	Hydralazine	Y	N
34.9	(If NO or UNKNOWN, skip to Q. 35 Specify:	·)			-		36.8	Open-label ACE inhibitor (Select "S" if in SOLVD trial)	Y	N
	EDICATIONS IN USE AT LAST HOSPITA	LI-		Yes	No		36.9	Digitalis	Y	N
	ATION OR OUT-PATIENT VISIT				••		36.10	Calcium antagonist	Y	N
35. I	Date of last hospitalization or ou	it-pat 7	ien	t vis	it:		36.11	Other vasodilator	Y	N
							36.12	Antihypertensive (other than above	e) Y	N
	Month Day Year						(conti	inued)		
36.1	Potassium-losing diuretic	Y	N							
	SOLVD MAIN REGISTRY BASELINE FORM (screen 13 of 15) (RBF page 7 of 8)									
		v.	-	No		T				

	Yes	No	
36.13	Other inotropic agent Y	м	39. Height (enter inches or cm):
36.14	Anticoagulant Y	N	39.1 in.
36.15	Insulin Y	N · .	
36.16	Steroids Y	N	39.2 cm.
36.17	Beta-2 agonist inhalers Y	N	beats/

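### Examination signs 43.1–43.5 on the chart-abstracted Registry Baseline Form have no Unrecorded code, so absent and not mentioned cannot be separated; any resulting bias is of uncertain direction.

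*Protocol*

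**What the plan says.** Section IX (Baseline Data Collection) has a research nurse fill in the Registry Baseline Form from the patient chart, and the instructions at the head of the form limit the abstractor to the medical records.

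Most sections of the form allow for a silent chart. The etiology items (24.x), trial-exclusion items (26.x) and clinical-history items (28.x) offer Yes, No and Unrecorded. So does the prior-surgery question (34.1): "balloon valvuloplasty? Y N U (If NO or UNRECORDED, skip to Q. 35".

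The physical-examination block does not. Its continuation header reads "Any of the following present? (cont.) Yes No", and its first item is "43.4 S3 gallop Y N".

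The X-ray findings (22.x) also appear as Yes/No, as far as the copy is legible, but a screening question comes first: "Is chest-X-ray available? Y". A No there skips the section. Next comes "22.1 Evidence of pulmonary congestion Y (If NO, skip to Q. 23", ahead of the individual findings such as "Alveolar or pulmonary edema" (22.4).

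Subsidiary objective 3 (Section II.B) is: "To relate other baseline covariates of prognostic importance to subsequent mortality and morbidity in the above population". On chart data in general, Section VII concedes that "it is possible that some of the data collected from the hospital records may be biased".

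**The concern.** With only Yes and No available, an abstractor whose chart says nothing about an S3 gallop has no printed way to say so. If No is circled, the variable measures whether the sign was charted as present, not whether it was present. The lost distinction cannot be recovered from the completed form by any later analysis.

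At stake are the prevalence of the five signs and their estimated relation to mortality and morbidity under subsidiary objective 3. The form handles the same problem properly elsewhere. Edema as history (28.11) can be coded Unrecorded, but edema on examination (43.2) stands under a Yes/No header, although the same nurse reads the same chart for both.

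**Working it through.** **1. Is the missing code only a page-edge artefact?** Several form pages are cut at the right edge in the copy read, so the reading rests on left-hand columns.
- Item 43.4 is in a left-hand column and shows Y and N only, under a Yes/No header.
- On the screen with items 22.4–22.5 and 24.x, item 22.5 (left) shows Y and N, while the etiology items beside it show Y, N and U.
- The codes for 43.2 and 43.5 are not legible in the copy. They are read from the block header.

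The absence of U is therefore real for the examination block.

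**2. A figure to anchor on.** The protocol states no figure on this point. To borrow realistic inputs, take Table 1, Case 11: 333 vs 333 patients, one-year mortality .06 vs .12, two-sided 0.05.
- Pooled SE = √(2 × .09 × .91 / 333) = .02218
- Unpooled SE = √((.06 × .94 + .12 × .88) / 333) = .02206
- Power = Φ((.06 − 1.96 × .02218) / .02206) = Φ(0.75) = 0.773

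The stated power is .77, so it reproduces. Case 11 compares ejection-fraction tertiles, and only its numbers are used here.

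**3. Non-mention unrelated to outcome, silence coded No.** The documents give no charting rate. Assume one-year mortality of 20% with the sign and 10% without (true RR 2.0), true prevalence *v*, and a share *r* of present signs charted. Then

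mortality in the No group = [v(1−r) × .20 + (1−v) × .10] / [v(1−r) + 1 − v], and observed RR = .20 / that.

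Example, v = .4 and r = .5: (.2 × .20 + .6 × .10) / .8 = .125, and .20 / .125 = 1.60.

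| Charted (assumed) | RR seen, prevalence 20% | RR seen, prevalence 40% |
|---|---|---|
| 90% | 1.95 | 1.88 |
| 70% | 1.87 | 1.71 |
| 50% | 1.80 | 1.60 |

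Observed prevalence falls to 90%, 70% or 50% of the truth.

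With the Case 11 inputs (prevalence 50%), 10%, 30% and 50% non-mention give RR 1.83, 1.62 and 1.50, with power 0.68, 0.51 and 0.36 instead of 0.77. These power figures apply only to a comparison of that size.

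**4. Non-mention related to severity.** Let the non-mention share differ between sign-positive patients who die and those who survive, as a stand-in for charting that tracks severity. Use mortality .06 vs .12 and prevalence 50%. The true cell proportions are: sign and died .06, sign and survived .44, no sign and died .03, no sign and survived .47.
- Non-mention 10% in deaths, 30% in survivors: Yes group .054 / (.054 + .308) = .1492; No group .036 / (.036 + .602) = .0564; RR = 2.64.
- Non-mention 30% in deaths, 10% in survivors: Yes group .042 / (.042 + .396) = .0959; No group .048 / (.048 + .514) = .0854; RR = 1.12.

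At 20% prevalence the same two patterns give 2.53 and 1.43. From a true 2.0 the error can go in either direction.

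**The case against.** **No coding rule is shown.** A reader might infer that every unmentioned sign is recorded as absent. The documents do not say so. The form points to general completion instructions, and item 31.2 to a Manual of Operations. Neither is shown, and a blank or a missing code is not excluded. This stands: what can be said is that No may be used for silence.

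**Direction.** A reader might also infer that effects are pulled toward none. That requires both coding as No and non-mention unrelated to outcome. If sicker patients are charted more fully, the ratio can be inflated instead. Section VII does not settle this, because its example concerns tests ordered in the sickest patients, not how fully signs are charted.

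**X-ray findings.** It is tempting to say that a stratifier of the primary objective is damaged too. The case is weak. Item 21.1 keeps a missing film from being coded as negative, Section V has uncertain films reviewed by a physician-investigator, the qualifying item 4.1 already offers Unrecorded, and the codes for 22.1–22.3 are cut off in the copy.

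**Safeguards.** The examination date (item 37) can identify a chart with no examination at all, but not an examination note that omits one sign. Section VII(b) collects the clinical data again directly in the Substudy in order to compare them with the chart. That can help measure the error, but it covers about 1000 of 6000 patients and leaves roughly 5000 uncorrected. The chart sign is taken at admission for hospitalized patients, while the Substudy visit may fall up to 90 days after enrollment. Rales or edema may truly have changed by then, so disagreement is not always chart error.

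**Conclusion.** The point holds for items 43.1–43.5. The form as printed cannot separate a sign found absent from one not mentioned, although it provides that code for most other abstracted items. The likely consequence is misclassification of covariates meant for subsidiary objective 3.

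Its size is not known from the documents. Under the assumed charting rates of 90% to 50%, with silence coded No and non-mention unrelated to outcome, a true RR of 2.0 appears as 1.95 to 1.60. At 20% prevalence the loss is modest (1.95 to 1.80). Where charting tracks severity, the direction is open, as the 2.64 and 1.12 examples show.

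The documents do not support saying that silence is always coded No, that bias toward the null is assured, or that the X-ray stratification of the primary objective is compromised. The all-cause mortality endpoint itself is not affected.

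**What to change.** Add the form's existing U code to items 43.1–43.5. It may also be added to 22.2–22.5, where the need is smaller. If the completion instructions already give undocumented signs a distinct code, printing that rule beside item 43 would serve equally well. A rule that silence means No would not.

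Report the unrecorded rate for each sign. In the prognostic models, analyse U as its own category, or show results with U taken as No and with U taken as missing. Treating U only as missing is not a safe default: if charting tracks severity, dropping those patients is selective. Use the Substudy re-examination as a partial check on the chart codes. Allow for the time gap and for the unequal sampling in Appendix D (100% of rare etiologies, 7–13% of ischemic patients).

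The cost is a third response box on five items (nine with the X-ray findings) and the matching data-entry change. Some signs will show a high unrecorded rate, which limits what can be claimed for them. Analysts who prefer to pool U with No can still do so.

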43.5 Mitrai regurgitation animi	
J. ECG FINDINGS (Latest ECG, but not within 72 hours of an MI; use only if taken within	51. Amplitude of S wave in V1:
Last 3 months)	52. Amplitude of S wave in V3:
Month Day Year	53. SI segment depression in inferior leads of V5 or V6:
Yes No	
45. Atrial fibrillation/flutter Y N (If YES, skip to Q. 47)	54. Is Q-wave MI present? Y (If NO, skip to Section K)
46. P wave terminal force in V1:	55. Location of MI: Anterior Inferior Both
47. QRS delay <= 120 ms? Y N (If NO, skip to Section K)	Unknown
48. Amplitude of R wave in V5 or V6:	

## SOLVD MAIN REGISTRY BASELINE FORM (screen 15 of 15) (RBF page 8 of 8)

SOLVD REGISTRY SUBSTUDY BASELINE FORM (screen 1 of 12) (RSB page 1 of 7)

A. IDENTIFYING INFORMATION	B. ECHOCARDIOGRAPHY ELIGIBILITY	Yes
<pre>1.1 Today's date:///</pre>	
 
3.1 Date 2D and M-mode echos done:
 
Month / Day / Year
 
3.2 Were these echocardiograms of good quality? (See protocol for criteria) (If NO, exit form)
 
3.3 Was Doppler echo done? (only for those participants in the Echo Substudy) (If NO, skip to Section C)
 
	Y Y
2.2 Participant's First Name: 2.3 Participant's Middle Initial:	3.4 Date Doppler done: /// Month Day Year	1

Т

c.	ETIOLOGY OF DISEASE AND NYHA CLASS			Yes
4.1	Indicate the primary etiology of the patient's heart disease (choose only ONE of the following):	5.	Indicate all of the following etiologies the have occurred (including the etiology specia bove):	nat ified
	Ischemic heart disease (HD) 1	5.1	Ischemic heart disease (IHD)	Y
	Hypertensive heart disease (HHD) 2	5.2	Hypertensive heart disease (HHD)	Y
	Active myocarditis 3	5.3	Active syocarditis	Y
	Valvular heart disease - aortic 4	5.4	Valvular heart disease - aortic	Y
	Valvular heart disease - mitral 5	5.5	Valvular heart disease - mitral	Y
	Idiopathic cardiomyopathy (specifics unknown) 6	5.6	Idiopathic cardiogyopathy (specifics unknown)	Y
	Specific cardiosyopathy (ax: viral, toxic, ETOH, postpartum, history of cocaine use) 7 (If none, skip to Q. 5)	5.7	Specific cardiomyopathy (ex: viral, toxic, ETOH, postpartum, history of cocaine use) (If NO, skip to Q. 6)	Y
4.2	Specify:	5.8	Specify:	
		6.	New York Heart Association CHF Class: (Choose only one)	

SOLVD REGISTRY SUBSTUDY BASELINE FORM (screen 3 of 12) (RSE page 2 of 7)

Contractor					
		Yes	No		Yes
D.	PAST CLINICAL HISTORY (up to completion			7.9 Hypertension	¥
	of the Registry Baseline form)			7.10 Peripheral vascular disease	Y
7.	Does the participant have a history of:		(restaut)	7.11 Edema	Y
7.1	Pulmonary edema	Y	М	7.12 Breathlessness on exertion	Y
7.2	Diabetes mellitus	Y	M	7.13 Asthma	¥
7.3	Chronic obstructive pulmonary disease	Y	N	(If NO, skip to Q. 8)	
7.4	Cerebrovascular accident	¥	N	7.14 Approximate duration of asthma:	] :
7.5	Angina pectoris	T	M	8. Cigarette smoking (ignore any other tobac	
7.6	Peripheral embolism	¥	M	8. Cigarette smoking (ignore any sther total 8.1 Has the participant ever smoked cigarette	
7.7	Pulmonary embolism	¥	N	regularly? (If NO, skip to Q. 9)	Y
7.8	Syncope	T	N		

•

•

т

8.2	At what age did the participant first begin to smoke cigarettes regularly?	Yes
	years of age	8.7 - After 24 years of age cigts/we
8.3	For how many years in total has the participant smoked regularly?	8.8 - During last 6 months cigts/we
	years	8.9 Did the participant smoke any cigarettes in the past week?
8.4	For how many of those years did the participant smoke filter-tipped cigarettes?	9. Alcohol consumption history
	What (approximately) was the largest number of	9.1 Has the participant ever consumed alcohol regularly?
	cigarettes the participant generally used to smoke in a week? (Count 1 oz of handrolled to- bacco as 28 cigarettes) -	9.2 Does the participant currently consume alcohol regularly?
8.5	- Before 20 years of age cigts/week	9.3 Last week, how many drinks did the participant have? (1 drink = 12 oz beer = 4-5 oz wine =
8.6	- From 20-24 years of age cigts/week	1.5 oz spirits) drinks

.

,

SOLVD REGISTRY SUBSTUDY BASELINE FORM (screen 5 of 12) (RSE page 3 of 7)

9.4	Specify current drinking pattern: Heavy H Regularly R Socially S Rarely X Unknown U GO TO Q.10.1		Yes No Unk Previous myocardial infarction? Y N (If NO, skip to Q. 11) Date of most recent myocardial infarction:
9. 5	Number of days a weak the participant used to drink:	10.3	Month Year Was the MI complicated by pulmonary edema, shock, or heart failure? Y N
9.6	Number of drinks the participant used to consume per week (1 drink = 12 oz beer = 4-5 oz wine = 1.5 oz spirits):	11. 12. 13.1	Permanent pacemaker? Y N Use of automatic implantable defibrillator? Y N Previous cardiac surgery, PTCA, or
9 .7	Specify former drinking pattern: Heavy N Regularly R Socially S Rarely X Unknown U		balloon valvuloplasty? Y N (If NO, skip to Section E)

SOLVD REGISTRY SUBSTUDY BASELINE (screen 6 of 12) (RSB page 4 of 7)

.

Yes	No	Unknown	E.	MEDICATIONS CURRENTLY USED	Yes
13.2 Date of most recent cardiac surgery, PTCA,			15.1	Digitalis	Y
or balloon valvuloplasty:			15.2	Other instropic agent	Y
	s		15.3	Potassium-losing diuretc	Y
Month Year			15.4	Potassium-sparing diuretic	Y
14. Type of cardiac surgery:	1004012-00		15.5	Antiarrhythmic drug other than	v
14.1 Coronary artery bypass graft Y	N	U		beta-blocker or calcium antagonist	•
14.2 Valve replacement - aortic Y	N	υ	15.6	Regular use of antiplatelet	Y
14.3 Valve replacement - mitral Y	N	υ	15.7	Beta-blocker	Y
14.4 Percutaneous transluminal coronary	~	U	15.8	Long-acting oral nitrate and paste	Y .
angioplasty (PTCA) Y	N	U	15.9	Hydralazine	. Y
14.5 Balloon valvuloplasty Y	N	υ	15.10		. Y
14.6 Other Y	N			(Select "S" if in SOLVD trial)	
(If NO, skip to Section E)			15.11	Calcium antagonist	. Y
14.7 Specify:			(conti	inued)	

SOLVD REGISTRY SUBSTUDY BASELINE FORM (screen 7 of 12) (RSB page 4 of 7)

a - 11	Yes	No	18. Heart rate:	beat
15.12 Other vasodilator	¥	N		
15.13 Antihypertensive (other than above)	¥	N	19. Systolic blood pressure:	mmHj
15.14 Anticoagulant	Y	N	20. Diastolic blood pressure:	em H i
15.15 Insulin	Y	N		
15.16 Staroids	Y	N	21. Are any of the following present?	Yes
15.17 Beta-2 agonist inhalers	Y	N	21.1 Rales	Y
15.18 Potassium supplements	Y	N	21.2 Edema	¥
			21.3 Elevated jugular venous pressure	Y
F. PHYSICAL EXAMINATION			21.4 S3 gallop	Y
16. Weight (enter 1bs or kg)	-		21.5 Mitral regurgitation sursur	Y
16.1 1bs OR 16.2	kg			
17. Height (enter inches or cm)	_			
17.1 in OR 17.2	] 📾			
	and a Constant	And in case of the local division of the loc		

SOLVD REGISTRY SUBSTUDY BASELINE FORM (screen 8 of 12) (RSE page 5 of 7)

Т

G.	ECG FINDINGS (Should be 72 or more hours after an MI)	26.	Amplitude of R wave in V5 or V6	 .
22.	Date ECG taken:		(whichever is larger):	ш .
	Month Day Year	27.	Amplitude of R wave in AVL:	$\Box$
23.	Atrial fibrillation/flutter? Yes No (If YES, skip to Q. 25)	28.	Amplitude of R wave in II, III, or AVF (whichever is larger):	
24.	P wave terminal force in V1:	29.	Amplitude of S wave in V1:	
25.	QRS delay <=120 ms?			······.

5

.

	SOLVD	REGISTRY SUBSTUDY BASELINE	FORM (screen 9 of 12) (RSB page 5 of 7)
	ST segment depression in inferior leads or V5 or V6:		Ye 36. Serial chest X-ray available to make determinations?
32.	Is Q-wave MI present? (If NO, skip to Section H)	Yes No	37.1 Evidence of pulmonary congestion? Y (If NO, skip to Section I)
3 3.	Location of MI:	Anterior A Inferior I Both B Unknown U	37.2 Basal or perihilar vascular blurring?       Y         37.3 Kerley B lines?       Y         37.4 Alveolar or pulmonary edema?       Y
Ħ.	X-RAY FINDINGS (Should be 7 or cardiac surgery, PTCA, or ball	r more days after an MI, loon valvuloplasty)	37.5 Pleural effusion? Y
34.	Date X-ray taken:	lear	
 
I. PROCEDURES
 
38. Was the Holter monitoring done?

35.	Cardiac thoracic ratio (pleas	10 Bessure):	Month Day Year

SOLVD REGISTRY SUBSTUDY BASELINE FORM (screen 10 of 12) (RSB page 6 of 7)

Т

ï

40. Neurohumoral measurements:	Yes	No	40.5 Were the neurohumoral measurements made in the morning or afternoon?
40.1 Was the PNE sample taken?	Y Y	N N	A (AM) P (PM) 40.6 Date samples sent to core laboratory: ////// Month Day Year
Month Day Year 40.4 Hour neurohumoral measurements taken (01-12):	:		TO BE COMPLETED LATER         40.7 PNE:       pg/ml         40.8 PRA:       ng/ml/hr

SOLVD REGISTRY SUBSTUDY BASELINE FORM (screen 11 of 12) (RSE page 6 of 7)

	Ye	3	No		Yes
41.	Were the procedures done on the same day the echocardiograms were taken? (If YES, skip to Section J)	¥	N	46. Indicate any of the following symptoms pr	resent:
				46.1 Angina	¥
42.	Did any major events occur in the interim? (If YES, complete Registry Hospitalization Fo	Y Form)	N	46.2 Dyspnea	¥
				46.3 Fatigue	Y
J.	SIX-MINUTE WALKING TEST			46.4 Dizziness	Y
43.	Did the participant finish the six-minute walking test?	¥	N	46.5 Syncope	Y
				47. Total distance travelled (enter feet or :	meters)
44.	Time completed:			47.1 ft OR 47.2	
45.	Were there any breaks in continuity? Y		N	•	

۱

ĸ.	LADDER OF LIFE	10
	Here is a ladder representing BEST the "Ladder of Life." The top POSSIBLE 10 represents the best possible LIFE 9 bottom represents the worst possible life for him/her. 8	
48.	On which step of the ladder does 7 the participant feel he/she is standing 6 at the PRESENT time? 5 4	N2
49.	On which step does the participant feel he/she was standing FIVE YEARS AGO?  2 WORST POSSIBLE 1 LIFE	
50.	On which step does the participant feel he/she will be standing FIVE YEARS FROM NOW?	

	- KEG	SISTRY
HC	SPITAL	ZATION FORM
~	A / 9-1-1986	
65.6 JH		BM: RHF VERSION: A COMMAN
Budber of Stors Sa	of farm has been used of of the first time the at clearly when entering a questions, circle the rm. Specific instruction (on the question. See	a contract participant has been hespitalized. The sequence musher is nevers to indicate the Sequence musher fars is used for the participant contacts of a response in the appropriate bases. e one appropriate letter corresponding to one for various purstions are enclosed in the SQLVD General Instructions for Completing
E · 1057	TALIZATION FORM (ser	ten 1 of 6 ) (MF page 1 of 4 )
A. TDENTIFYING INFORMATION 1. Today's Date:/	,,/□	4.2. Bate of Discharge:
2.1. Last Home:		B. PRIMARY REASON FOR MOSPITALIZATION S. Mospitalization
E.E. First Name:		Cardiovascular C Goncordiovascular G
2.3. Riddle Name:		if Cardiovascular (C), go ta Buestion 7. on page 2. 6. If Roncardiovascular (R), specify:
3. Semitet Neer		
4.1. Bate of Admissions	⊥,'⊥ ∂ey ,' tear	de te section C. SECONSART SEASONS FOR SOSPITALIZATION, Suestion 11. on page 3. 6.1 NgCDA coding

· ·

DDE		REASON	EODE		REASON		
A	•	Versening CHF	H ·	•	Other arrhythaias		1.
3	•	iles Dif	1 -	•	Stroke		
C		Horsening or new angina	1	•	Cardiac surgery	•	
)	•	Hyscardial Infarction	K.		Pulsonary embolism		
E	•	Houfatal cardiac arrest or	1.		Peripheral emplisa		
		ventricular tachycardia that required deribrillation	K •	•	Nypetension		
F	•	Súpraventricular techycerdia	1 .	•	Azotonio		
		or Tibrillation that required BC conversion or pacing	0		Any other major event		
8	•	Uncertain tachycardia that required DC conversion or pacing	•	•	Dig toxicity		1
		Hotes If PRIMARY REASON = Myscardial infarcti	ion (D) gi		is Ausstian 8.a.	a de la construcción de la construc	
		IT PRIMARY REASON = Cardiac surgery (3)	) go to D		stion 9.1.		
		IT PRIMARY REASON = Any other major eve	ent (0) s	. 1	te Questian 10.		

Stherwise, go to section C. SECONDARY REASONS FOR HOSPITALIZATION, Question 11. on page 3.

.

T + HOSPITALIZATION FORM (screen 3 of 6 ) (RHF page 2 of 4 )

Hypcardis! Infarction (HI) If Yes, indicate the fallowing:			Cardiac Surgery 9.1. If Yes,	
8.a. Jote of HI:			indicate surgeryBraft (CABG) 6 Valve V Transplantation T	
Bude Time of HI2 a)			Braft & Valve B Dther D	
		•	If Graft (6), Valve (V), Transplantation (T) or Graft & Transplant (B), go to Buestion 11., page 3	
p.c Indicate the prosence of the follo	1	•	9.2. If Other (D), specify:	]
8.1. Pail	Yes Y		The to Buestian 11. an page 3.	
8.2. Elevated enzymes	۲	u ا	Any Other Major Event	_
8.3. Changes in ECS		* U	10. If Yes, specify other sajor event:	
an a			i HECZA Coding	Ĺ
HOSPIT	LIZATION FORM	(screen 4 of 6 ) (AVF page 2 of 4 )		
--	------------------------	--		
C. SECONDARY REASONS FOR HOSPITALIZATION	ĩ	Yes No. 14. New CHF		
11. Hespitalization		I 4. Men CHP		
Cardiovascular	2	15. Morsening ar new angina		
Newcardiovascular Now	E A	16.1. Nyscardial Infarction (HI)		
	•	If No (Hyscardial Inforction), go to Question 17.		
If Cardiovascular (C), as to Aug	stian 13.			
If None (D), go to section D. IN PERSON COMPLETINE THIS FORM, Que on page 4.	ITIALS OF stion 28.	14.1a. Date of HI:/		
2. If Noncardiovascular (N), specify:		16.16. Tise of HI: (Trund if the (Trund if the (		
12. HICHA coding		b) 8.8 A		
So to section D. INITIALS OF PERS THIS FORM, Question 28. on page 4	ION COMPLETING	I Indicate the presence of the filler. 3		
Indicate SECONDARY REASONS:		Yes No (		
Yes	No	16.2. Pam		
. Worsening CHF		16.3. Elevated enzymes		
	IZATION FORM	(screen 5 of 6 ) (RHF page 3 of 4 ) 22.2. If Yes (cardiac surgery), indicate the typeGraft 6		
.4. Changes in EES	T B	U Valve V		
		Transplantation T		

 
Nonfatal cardiac arrest ar ventricular tachycardia
 
		Graft & Valve B		
that required defibrillation	ч н	Sther O		

 
Bupraventricular tachycardia
 
or fibrillation shat required
 
AC conversion or pacing
 
		If Braft (6), Valve (V), Transplantation (T) pr Braft & Transplant, go to Bustion 23.		
. .		22.3. If Sther (S), specify:		
Becrtain techycardia     that required	• -			
R conversion or pacing	T H			
. Other arrhythaias	Y H			
Strate	Y B	Yes No 23. Pulmonary embolise		
1. Cardiac surgery	Y H	24. Peripheral esbolisa		
If the (Cardiac surgery), go to 8	westion 23.			
		25. Hypotensian		

	Yes	No		
A:pt86ia	۲		•	
Any other sajer event	Y	N	j Øl	
If No (sajor event), go to dues	tion 28.			
If Yes, specify other eajor events	1		12	125.1
HICDA coding [		H	(34 -	
ITIALS OF PERSON MPLETING THIS FORM				
Ritials	Ľ	$\Box$		
		•		

÷

.

